7.9 EXPLORATORY ANALYSIS

7.9.1 BIOMARKER AND GENOMIC DATA ANALYSIS

Summary statistics of biomarkers and genomic markers (including ctDNA, Cytokines, CyTOF and RO) will be reported by dose group or pooled and examined for possible associations with Investigator assessed RECIST efficacy endpoints (this will be done by running analyses of the efficacy assessment, grouped by biomarker categories, if deemed relevant and enough data per subgroup) and listed.

A separate plan for Biomarker statistical analysis, containing all the details of the planned analyses will be created.

8. INTERIM ANALYSES

Phase 1 (Dose Escalation)

Each dose escalation step is considered to be an interim analysis, but without a formal interim analyses report. The BLRM will be updated with the respective number of patients treated and the number of DLTs observed in the last cohort. The updated model will then give a statistical recommendation for the next escalation step. In addition, a risk-benefit assessment that includes a comprehensive analysis of safety and available clinical information will be done to decide on the next escalation steps. SRC will review the data at this stage and make the final decision regarding the dose escalation. A separate SRC charter will be composed to describe the SRC activities.

In case of a CTCAE Grade 5 adverse event or a second CTCAE Grade 4 adverse event at least possibly related to AFM24 at any time during Phase 1, the Sponsor will suspend further enrollment and an interim safety analysis will be done. The interim safety analysis will be submitted to the applicable competent authorities for review prior to resuming the study.

Phase 2a (Dose Expansion)

An interim analysis will be performed for each cohort independently, once the defined number of subjects (11, 15, and 15 subjects for Cohorts A, B, and C, respectively) in the respective cohort have completed their first post-baseline assessment and its confirmation (2nd post baseline assessment, ie, ≥ 12 weeks post-baseline) to be categorized under the primary response endpoint or have withdrawn from the study. Each cohort will be then assessed for futility and recruitment will not be stopped until the IA is completed. The results from this IA will be non-binding, unless no signs of efficacy are observed. Safety criteria will also be evaluated to decide on the continuation of the cohorts. Since this is a non-comparative multiple arm study no adjustment for multiple testing is made.

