7.2.11 Disease Response Assessment

Disease response will be assessed by the Investigator, using local RECIST v1.1 (Eisenhauer et al., 2009; Schwartz et al., 2016) and Response Evaluation Criteria in Solid Tumors for immunotherapy (iRECIST) (Seymour et al., 2017). In Phase 1 and 2a, imaging results will also be sent for independent central review. Tumor assessment with CT and/or MRI will occur at Screening as well as at timepoints specified in the SoA tables (APPENDIX A [Section 14.1] for weekly dosing schedule and APPENDIX B [Section 14.2] for q2w dosing schedule). Partial or complete response needs to be confirmed with repeated assessment at least 4 weeks after the initial assessment.

If initial radiological progressive disease is observed, while the clinical condition of the subject is stable, treatment continuation is allowed at the discretion of the Investigator. If treatment is continued after initial progressive disease, a confirmatory scan should be acquired within 4 to 6 weeks. However, the first successive scheduled timepoint after the confirmatory scan may be skipped if the window is considered not clinically relevant (up to the discretion of the Investigator).

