9.3.8.2 Phase 2a (Dose Expansion)

An IA will be performed for each cohort independently, once the defined number of subjects (11, 15, and 15 subjects for Cohorts A, B, and C, respectively, – see [Table 10](#)) in the respective cohort have completed their first post-baseline assessment and its confirmation (2nd post-baseline assessment, ie, ≥ 12 weeks post-baseline) to be categorized under the primary response endpoint or have withdrawn from the study. Each cohort will be then assessed for futility. The results from this IA will be non-binding, unless no signs of efficacy are observed. Safety criteria will also be evaluated to decide on the continuation of the cohorts. During the conduct of the study, after the interim analysis for Cohort A and C and stopping these cohorts for futility, it was considered unlikely that the continuation criteria can be met in Cohort B. Hence it was decided to prematurely stop enrollment after 8 patients in Cohort B.

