9.4.2 Phase 2a (Dose Expansion)

An optimum Simon's two-stage design will be used for the expansion phase ([Simon 1989](#)). The assumptions and sample size calculations for different cohorts are summarized in [Table 10](#).

Table 10: Sample Size Consideration for Expansion Cohorts

Indication	Objective Response Rate		Interim Analysis		Final Analysis		One-sided test	
	Alternative hypothesis	Null hypothesis	Number of subjects	OR, that may lead to stop	Number of subjects*	OR (rejection of the null hypothesis)	Power	Type I error rate (α)

RAS wt, microsatellite stable CRC	25%	5%	11	≤ 1	39	≥ 4	80%	5%
ccRCC	30%	14%	15	≤ 2	41	≥ 10	81%	5%
NSCLC EGFRmut	30%	14%	15	≤ 2	41	≥ 10	81%	5%
Maximum number of subjects: 121								

ccRCC = clear cell renal cell carcinoma; CRC = colorectal cancer; EGFRmut = epidermal growth factor receptor mutant; NSCLC = non-small cell lung cancer; OR = objective response; RAS = rat sarcoma gene; wt = wild type.

*Up to a total of N~40 subjects per cohort according to the [FDA guideline, 2018](#)

In other words:

RAS wt,
microsatellite
stable CRC: The power that is computed at ORR=25% (alternative hypothesis) is 80%. If the treatment is actually not effective, there is a 0.05 (α) probability of concluding that it is. After testing the treatment on 11 subjects in the first stage, the study may be terminated if 1 or fewer responds. At final analysis (N=39) if the total number responding is less than or equal to 3, the treatment is rejected.

ccRCC: The power that is computed at ORR=30% (alternative hypothesis) is 81%. If the treatment is actually not effective, there is a 0.05 (α) probability of concluding that it is. After testing the treatment on 15 subjects in the first stage, the study may be terminated if 2 or fewer responds. At final analysis (N=41), if the total number responding is less than or equal to 9, the treatment is rejected.

NSCLC
EGFRmut: The power that is computed at ORR=30% (alternative hypothesis) is 81%. If the treatment is actually not effective, there is a 0.05 (α) probability of concluding that it is. After testing the treatment on 15 subjects in the first stage, the study may be terminated if 2 or fewer responds. At final analysis (N=41), if the total number responding is less than or equal to 9, the treatment is rejected.

The sample size is based on the safety analysis set for all subjects.

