- o. Urinalysis parameters include glucose, protein, bilirubin, ketones, blood, pH, specific gravity (microscopic examination when indicated), FSH (to confirm post-menopausal status [Screening], and human chorionic gonadotropin (female pre-menopausal subjects [Screening] (See [APPENDIX D](#), Section [14.4](#)).
- p. Coagulation may be assessed from the hematology sample.

- q. Tumor biopsy for central analysis is required for subjects in the dose escalation phase (Phase 1) only.
- r. +1 week: The second tumor biopsy will be performed on a non-dosing day during week 3 (+1 week).
- s. CT or MRI will be done at Screening and during the last week of cycles 2, 4, 6, 8, and every 3 cycles thereafter.
- t. During pre-screening, only AEs which are related to study procedures are to be recorded. AEs occurring after signing of the Main ICF but prior to the first dose of study drug should be recorded on the Medical History eCRF page (**Note:** any SAEs which are related to study procedures and occur during pre-screening and any SAEs that occur following signing the Main ICF and prior to the first dose of study drug will still be reported using the SAE form). Please also refer to Section 8.1.3 for detailed description.
- u. Concomitant medications administered after the Safety Follow-up visit should be recorded for SAEs which are considered related to study drug.

ADA = anti-drug antibodies; C = cycle; CT = computed tomography; ctDNA = circulating tumor DNA; D = day; ECG = electrocardiogram; ECOG PS = Eastern Cooperative Oncology Group Performance Status; EGFR = epidermal growth factor receptor; EOI = end of infusion; EOT = End of Treatment visit; FSH = follicle-stimulating hormone; HIV = human immunodeficiency virus; I/E = inclusion/exclusion; ICF = informed consent form; LT-FU = long term follow-up; MRI = magnetic resonance imaging; PD = pharmacodynamics; PK = pharmacokinetics; SCR = screening; S-FU = Safety Follow-up visit.

Table 12: Schedule of Pharmacokinetic, Pharmacodynamic, Immunogenicity, and Translational Assessments for Weekly AFM24 Dosing Regimen (Without Split Dosing) - For Phase 1

Sample	SCR	Cycle 1												
		D1			D3		D7	D8	D15	D22			D24	D28
		Pre	EOI ^a	+1h EOI ^a	+48h EOI ^a	+2h	+144h EOI ^a	Pre	Pre	Pre	EOI ^a	+1h EOI ^a	+48h EOI ^a	+144h EOI ^a
PK		X	X		X	X	X	X	X	X	X	X	X	X
ADA ^b		X					X	X	X					
CD16a RO	X				X					X			X	
PD (circulating lymphocytes)		X		X	X			X	X	X		X	X	
PD (cytokines) ^c		X	X		X			X	X	X	X		X	

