- m. Urinalysis parameters include glucose, protein, bilirubin, ketones, blood, pH, specific gravity (microscopic examination when indicated), FSH (to confirm post-menopausal status [Screening], and human chorionic gonadotropin (female pre-menopausal subjects [Screening] (See APPENDIX D, Section 14.4)).
- n. Coagulation may be assessed from the hematology sample.
- o. CT or MRI will be done every 8 weeks after baseline assessment for first 4 assessments, and every 12 weeks thereafter.
- p. Concomitant medications administered after the Safety Follow-up visit should be recorded for SAEs which are considered related to study drug.
- q. Only taken in Cycle 2 at sites that can perform the PBMC isolation according to the lab manual/Sponsor requirements.
- r. During pre-screening, only AEs that are related to study procedures are to be recorded. AEs occurring after signing of the Main ICF but prior to the first dose of study drug should be recorded on the Medical History eCRF page (**Note:** any SAEs that are related to study procedures and occur during pre-screening and any SAEs that occur following signing the Main ICF and prior to the first dose of study drug will still be reported using the SAE form). Please also refer to Section 8.1.3 for detailed description.

ADA = anti-drug antibodies; C = cycle; CT = computed tomography; ctDNA = circulating tumor DNA; D = day; ECG = electrocardiogram; ECOG PS = Eastern Cooperative Oncology Group Performance Status; EGFR = epidermal growth factor receptor; EOI = end of infusion; EOT = End of Treatment visit; FSH = follicle-stimulating hormone; HIV = human immunodeficiency virus; I/E = inclusion/exclusion; ICF = informed consent form; LT-FU = long term follow-up; MRI = magnetic resonance imaging; PD = pharmacodynamics; PK = pharmacokinetics; SCR = screening visit; S-FU = Safety Follow-up visit.

Table 17: Schedule of Pharmacokinetic, Pharmacodynamic, Immunogenicity, and Translational Assessments for Every 2 Weeks AFM24 Dosing Regimen (Without Split) - Phase 2a Only

Samples	Cycle 1							Cycle 2							Subsequent Cycles		EOT ^f
	D1				D3	D15	D1+1					D3+1	D15±1	D1+1			
	Pre	+2h SoI	+4h ^a SoI	EOI ^b	+48 h EOI		Pre	Pre	+2h SoI±15 min	+4h ^a SoI±15 min	EOI ^b	+48h EOI		Pre	Pre	±2 days	
	-2h max	±15 min	±15 min	+15 min	±2h		-2h max	-2h max	SoI±15 min	SoI±15 min	+15 min	±2h		-2h max	-2h max		
PK	X			X	X	X	X	X			X	X	X	X	X	X	
ADA ^c	X						X	X						X	X	X	
PD (circulating lymphocytes) ^d	X			X	X		X	X			X	X		X			

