Primary endpoint for this phase will be Overall response rate (complete response [CR] + partial response [PR]) assessed by local RECIST v1.1. Best confirmed overall response will be used to define the ORR. The table below summarizes the confirmation rules:

Response at first visit	Response at consecutive visit (at least 4 weeks after the initial assessment)	Confirmed Response at visit
CR	CR	CR
CR	PR	PD
CR	SD	SD*
CR	PD	PD
PR	CR	PR
PR	PR	PR
PR	SD	SD*
PR	PD	PD
SD	CR	SD*

CONFIDENTIAL

Page 15 of 22

Statistical Analysis Plan template version 1.0 dated 27-MAR-2019

SD	PR	SD*
SD	SD	SD*
SD	PD	PD

CR = complete response; PD = progressive disease; PR = partial response; SD = stable disease

* - In order to assign Stable Disease as a confirmed response, there has to be another assessment of at least SD no less than 7 weeks after the initial visit. If this criterion is not satisfied, assign PD.

If the closest consecutive visit is closer than 4 weeks, or is not evaluable, use the next available assessment for confirmation. The last visit has no confirmed response. For iRECIST data similar approach will be used to define the confirmed response at visit.

Simon's two-stage design will be used to determine the outcome of the study in each of the three cohorts. The table below shows the decision thresholds for the design for all three cohorts:

Indication	Interim Analysis		Final Analysis	
	Number of subjects	OR, that may lead to stop	Number of subjects*	OR (rejection of the null hypothesis)
RAS-wt, microsatellite stable CRC	11	≤1	39	≥4
ccRCC	15	≤2	41	≥10
NSCLC EGFRmut	15	≤2	41	≥10

CRC = colorectal cancer; EGFRmut = epidermal growth factor receptor mutant; RAS-wt = rat sarcoma genes-wild type; NSCLC = non-small cell lung cancer; OR = objective response

*Up to a total of N~40 subjects per Cohort

The final analysis will take place after the last expansion arm was closed for futility or the last patient of the last expansion arm had the final end-of-study visit. Summaries will include the count and percentages of different best confirmed overall responses for each cancer type and observed ORR. In the final analysis, a p-value using the exact binomial test will be calculated comparing the response proportion to the probability stated under H_0 for each indication separately.

Listing of CT scan data, reporting both confirmed and unconfirmed responses at all visits will be created. Additionally, biopsy data will be listed.

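### At the Phase 2a futility look, a response first seen at a subject's second and latest scan counts as a non-response, although the Simon sizing treats every stage 1 response as known

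*SAP*

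**What the plan says.** **Timing.** SAP 8 triggers the look when the stage 1 subjects (11, 15 and 15 in Cohorts A, B and C) have "completed their first post-baseline assessment and its confirmation (2nd post baseline assessment", at 12 weeks or more, or have withdrawn. Protocol 9.3.8.2 has the same trigger: "completed their first post-baseline assessment and its confirmation (2nd post-baseline assessment".

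**Scans.** On weekly dosing, "CT or MRI will be done at Screening and during the last week of cycles 2, 4, 6, 8, and every 3 cycles thereafter" (Protocol Appendix A). On two-weekly dosing, "CT or MRI will be done every 8 weeks after baseline assessment for first 4 assessments, and every 12 weeks thereafter" (Appendix B). Either way, the first scheduled scans fall at about weeks 8, 16 and 24.

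**What counts.** "Partial or complete response needs to be confirmed with repeated assessment at least 4 weeks after the initial assessment" (Protocol 7.2.11). SAP 7.7.1 defines the response rate by best confirmed response. Its table classes stable disease followed by PR or CR as stable disease, and adds: "The last visit has no confirmed response".

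**Boundary.** For Cohort A, "After testing the treatment on 11 subjects in the first stage, the study may be terminated if 1 or fewer responds" (Protocol 9.4.2). Cohorts B and C may stop at 2 or fewer of 15. Table 10 uses one response rate per hypothesis for both stages.

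**Force.** SAP 8 and Protocol 9.3.8.2 make the look non-binding unless there is no sign of efficacy, a term that neither document defines. SAP 8 keeps recruitment open until the look is complete.

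**The concern.** Calling the second scan the confirmation of the first fits a subject whose response was already visible at scan 1. It does not fit a subject with stable disease at scan 1 and PR at scan 2. That subject's confirmatory scan is still to come when the look is taken, and the count records no response.

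The boundaries are 1 and 2 responders, so one uncounted response can decide a cohort. The error runs only one way: the stage 1 count can be too low, never too high. The stated power rests on a count with no such loss.

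**Working it through.** **Inputs from Protocol 9.4.2.** Cohort A: n1 = 11, stop at ≤1, N = 39, success at ≥4, rates 5% and 25%. Cohorts B and C: n1 = 15, stop at ≤2, N = 41, success at ≥10, rates 14% and 30%.

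**Assumed inputs, not in the documents.** k is the number of stage 1 subjects with only two scans at the look. f is the share of eventual confirmed responders whose response first appears at scan 2 or later.

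**Step 1: the plan's own figures (k = 0 or f = 0).** Stop probability = P(Bin(n1, p) ≤ r1). Power = sum over x > r1 of P(Bin(n1, p) = x) × P(Bin(N − n1, p) ≥ r + 1 − x), where r1 is the stage 1 limit and r the largest final count that fails.

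- Cohort A at 25%: stop = 0.0422 + 0.1549 = 19.7%; power 80.2%, which reproduces the stated 80%; type I error 4.77%.
- Cohorts B and C at 30%: stop = 0.0047 + 0.0305 + 0.0916 = 12.7%; power 76.8%; type I error 4.44%. The stated 81% does not reproduce with the stop followed. That is a separate point, and 76.8% is the baseline here.
- Cohort A with the look ignored: power 99.4%, type I error 12.9%. The stated 80% and 5% therefore presuppose that the stop is followed.

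**Step 2: the look as written.** A two-scan subject is counted with probability p(1 − f), any other subject with probability p. Uncounted responders re-enter at the final analysis if the cohort continues.

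Example: Cohort A, k = 3, f = 30%. For the 8 other subjects, P(0) = 0.1001 and P(1) = 0.2670. For the 3 two-scan subjects, the counted rate is 0.25 × 0.7 = 0.175, so P(0) = 0.5615 and P(1) = 0.3573. Stop = 0.1001 × (0.5615 + 0.3573) + 0.2670 × 0.5615 = 0.0920 + 0.1499 = 24.2%.

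| Cohort | k | Stop, f = 10% | Stop, f = 30% | Power, f = 10% | Power, f = 30% |
|---|---|---|---|---|---|
| A | 0 | 19.7% | 19.7% | 80.2% | 80.2% |
| A | 3 | 21.1% | 24.2% | 78.8% | 75.7% |
| A | 6 | 22.7% | 29.5% | 77.2% | 70.5% |
| A | 11 (upper bound) | 25.4% | 40.2% | 74.5% | 59.8% |
| B, C | 0 | 12.7% | 12.7% | 76.8% | 76.8% |
| B, C | 3 | 13.7% | 16.0% | 76.0% | 74.4% |
| B, C | 8 | 15.6% | 22.9% | 74.7% | 69.1% |
| B, C | 15 (upper bound) | 18.6% | 36.1% | 72.4% | 58.1% |

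The upper-bound rows need near-simultaneous enrolment. Subjects enrolled more than about 8 weeks before the last one will usually have reached scan 3 by the time of the look.

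**Step 3: if only a count of zero forces a stop.** This takes absence of any sign of efficacy to mean no counted responder, which is an assumption. With k = 3 and f = 30%, that probability moves from 4.2% to 5.6% in Cohort A and from 0.5% to 0.7% in Cohorts B and C.

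**The case against.** The strongest reply is that the stop is not automatic. The count only may lead to stopping, the look is non-binding unless there is no sign of efficacy, and an unconfirmed PR at scan 2 could fairly be read as such a sign. The sponsor could then continue. This stands as a limit on the size, and Step 3 shows how small the effect is if only a zero count compels a stop. It does not remove the gap. The text does not say whether a pending response is a sign of efficacy, and the stated error rates assume that the boundary is followed.

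A second reply is that a subject awaiting a confirmatory scan has not yet been categorised under the primary endpoint, so the look is not yet due. The trigger, however, is met by the second assessment itself, and SAP 7.7.1 gives the latest visit no confirmed response.

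Three stronger readings are tempting, and the documents do not support them:

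- **That Cohort A or C was wrongly stopped.** The protocol synopsis says only that they did not meet the continuation criteria on objective response. No counts are given, and no pending response is reported.
- **That the plan expects late responses.** iRECIST is exploratory, and treatment past initial progression is at the investigator's discretion. Neither predicts late RECIST v1.1 responses.
- **That power falls to about 60%.** That needs every stage 1 subject to be at two scans and f = 30%.

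**Conclusion.** The point holds as a defect in the counting rule. The timing, the classification and the direction of the error follow from the text. With the boundary followed, any k above 0 and f above 0 raises the chance of stopping an active drug.

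The size cannot be fixed from the documents. Under the illustrative k = 3 and f = 10% to 30%, the stop probability rises by 1.4 to 4.5 points in Cohort A and by 1.0 to 3.3 points in Cohorts B and C. If the sponsor uses its discretion to continue when a response is pending, the effect is smaller.

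Cohorts A and C have been stopped and Cohort B closed to enrolment at 8 subjects. The remaining practical use is a check of the stage 1 counts in A and C.

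**What to change.** Add to SAP 8 and Protocol 9.3.8.2: a CR or PR first seen at the subject's most recent scan is pending. The futility boundary is met only if confirmed plus pending responders are at or below it (1 of 11; 2 of 15). Otherwise the decision waits for the confirmatory scan at least 4 weeks later.

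The cost arises only when a pending response could change the decision. The look then waits 4 to 8 weeks, and a few more subjects may be enrolled, because recruitment already stays open. Passing stage 1 still requires confirmed responders, so the type I error stays within the design's 4.77% and 4.44% if the boundary is followed. The rule does not recover first responses at scan 3 or later, so it removes only part of the loss shown in the table.

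For Cohorts A and C, report the number of pending responses at the look and the stage 1 count after confirmation, without implying that either stop was wrong. The data are at hand: SAP 7.7.1 already lists confirmed and unconfirmed responses at every visit.

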9. DEVIATIONS FROM ANALYSIS AS DESCRIBED IN THE PROTOCOL

Apart from the above mentioned change, the planned analyses as described in this SAP do not deviate from the description in the protocol of the analyses to be performed.

10. PROGRAMMING SPECIFICATIONS

All outputs will be produced using SAS version 9.4 or a later version.

The margins should be at least 1.50 inches for the binding edge and 1.0 inches for all others.

In the top left portion of each table/listing, the *protocol number* will be presented. On the next line a *table/listing number* followed by the *title* of the table/listing and *population* information will be displayed. Horizontal lines will appear after the column heading of the table/listing. *Footnotes* will be put under the main body of text at the bottom of the page. The source listing number will be displayed for all tables. The *SAS program name* will appear bottom left in a string and the *page number* will appear on the bottom right corner of each table/listing. The *date and time of creation* of table/listing will appear bottom left under to the SAS program name line.

Courier New 8-point bold font will be used for all tables and listings. Usually, a landscape layout is suggested for both tables and listings, but it is not mandatory. Any date information in the listing will use the date9 format; for example, 07MAY2002.

The list of tables, figures, and listings (TFLs) is given in section below. Shells for unique tables and listings are provided in a separate Mock-Up TFLs document.

For details regarding the BLRM (Bayesian logistic regression model) for dose escalations in the phase I part as part of the SRC, updated standard deviation prior parameter and updated scenarios, please refer to the Protocol.
